2.7.4.2 Vital signs

Vital signs will be assessed at the scheduled visits in accordance with the Schedule of Study Assessments. All summaries of data will be based on the SAF.

Observed values as well as change from baseline values will be summarized at each scheduled visit through the end of Follow-up Period 1 using descriptive statistics for systolic blood pressure, diastolic blood pressure, respiratory rate, temperature, pulse, and pulse oximetry.

Vital sign results will be flagged as clinically significant if they meet the pre-specified criteria which are defined in Appendix 5.6. The number and percentage of patients meeting each clinically significant criterion through the end of Follow-up Period 1 will be summarized. A second output will be produced to detail post-baseline, post-OAV101 treatment values meeting each clinically significant criterion. In this second summary, only vital sign values reported on/after OAV101 dosing (during Treatment Period 1 and through the end of study for participants originally randomized to OAV101, during Treatment Period 2 and through the end of study for participants originally randomized to sham administration) will be considered. A listing of all clinically significant vital sign values will also be produced.

2.7.4.3 Anthropometry

Anthropometry will be assessed at the scheduled visits in accordance with the Schedule of Study Assessments. All data will be summarized using the SAF.

Observed values as well as change from baseline values through the end of Follow-up Period 1 will be summarized at each scheduled visit for body height as derived from tibial length, weight, and BMI.

2.7.4.4 Neurological examination and Sensory Nerve Action Potential

The incidence of abnormal findings occurring post-baseline and through the end of Follow-up Period 1 resulting from abnormalities in the sensory examination will be summarized by treatment group using the SAF.

A listing of neurological examination data collected through the end of study will also be produced.

To complement neurological examination, sural and radial sensory nerve action potential (SNAP) will be assessed. SNAP parameters consist of the overall interpretation (present, absent, unable to obtain) for both the right and left limbs. These data, as collected for all participants at Screening, will be summarized by treatment group using the SAF. Post-treatment, SNAP will be performed if there are sensory abnormalities in the neurological examination.

A listing of all SNAP data collected through the end of study will also be produced.

CCI

CCI

• CCI

• CCI

• CCI

• CCI

• CCI

CCI

• CCI

• CCI

- CCI
- CCI

• CCI

60

1

. CCI

• CCI

. cci

10

1

[figure not shown]
1

1

CCI

CCI

- CCI

CCI

- CCI
- CCI

Horizontal bar chart showing the distribution of CCI values across 10 categories. The x-axis represents the CCI value, ranging from 0 to 100. The y-axis lists 10 categories. Each category has a black bar representing the CCI value. The bars are ordered from highest to lowest CCI value.

Category	CCI Value
1	85
2	80
3	75
4	70
5	65
6	60
7	55
8	50
9	45
10	40

CCI [REDACTED]

CCI [REDACTED]

CCI [REDACTED]

- CCI [REDACTED]
- CCI [REDACTED]
- CCI [REDACTED]
- CCI [REDACTED]
- CCI [REDACTED]
- CCI [REDACTED]
- CCI [REDACTED]
- CCI [REDACTED]
- CCI [REDACTED]

CCI [REDACTED]

CCI [REDACTED]

CCI [REDACTED]

2.13 Interim analysis

No formal interim analysis is planned for this trial.

3 Sample size calculation

The sample size calculation is primarily based on the primary variable, change from Baseline in HFMSE total score.

CCI [REDACTED]

[REDACTED]

[REDACTED]

CCI

Assuming a true treatment difference in the change from Baseline in HFMSE of 3 points and a standard deviation of 5 points, a sample size of 125 participants (75 in the OAV101 treatment group and 50 in the sham procedure group) provides approximately 90% power that the primary analysis will be statistically significant at the two-sided 5% alpha level assuming a minimal number of participants prematurely withdraw from the study prior to Week 52. In addition, assuming a larger treatment difference in the change from Baseline in HFMSE total score of 5 points and the same standard deviation as anticipated in the overall study population (5 points) in the ≥ 2 to < 5 years old group, a sample size of 65 participants (39 in the OAV101 treatment group and 26 in the sham procedure group) could achieve $> 95\%$ power in this younger age group.

Because this is the first OAV101 clinical trial to include the RULM assessment, there are no historical data available upon which to base sample size calculations on.

In the AVXS-101-CL-102-IT clinical trial, the HFMSE responder endpoint was defined as the achievement of improvement in HFMSE of ≥ 3 points at any post baseline time point (through Month 12): 11/12 (91.7%) patients treated with OAV101 achieved response, compared to 2/15 (13.3%) patients in the Pediatric Neuromuscular Clinical Research (PNCR) group. For the current study, the responder endpoint is defined as the achievement of improvement in HFMSE of ≥ 3 points at the end of follow-up period 1 (and will be based on the average of the HFMSE scores at Month 11 and Month 12). Applying this same definition to the AVXS-101-CL-102-IT data, 9/12 (75%) patients treated with OAV101 achieved response. For PNCR, HFMSE was assessed less frequently (the last 2 time points of relevance were Month 9 and Month 12). Considering just the PNCR patients with HFMSE data at Month 9 and/or Month 12, then based on the average of these 2 scores or based on the single available score, 2/15 (13%) achieved response. The power to detect a significant difference in the ≥ 2 to < 5 year age group in this study, assuming a response rate of 75% for OAV101 and 13% for sham and alpha=0.05, would be $> 99\%$ with the planned sample size of N=65 patients (39 in OAV101, 26 in sham).

4 Change to protocol specified analyses

- The change in HFMSE from baseline over 52 weeks incorporating natural history data by MAP analysis in ≥ 2 to < 18 years overall study population is removed. This is because the study is fully enrolled, there is less value added to perform such analysis.
- The endpoint, proportion of participants showing changes (increase, decrease, no change) on 1 to > 5 HFMSE task (item) is removed from the SAP as the analysis concerning proportion of participants showing changes (increase, decrease, no change) at each individual HFMSE item provides more relevant information from clinical perspective.

5 Appendix

5.1 Imputation rules

Missing values for safety endpoints, including but not limited to AEs and laboratory values, will not be imputed. For local lab, missing units or normal ranges will be reviewed by the medical team. If any missing information needs to be imputed for selected lab tests, the imputed information will be captured in a Note to File.

5.1.1 Start and end dates for AEs and concomitant medications (CM)

Missing or incomplete adverse event and concomitant medication start and end dates will be imputed according to standard Novartis imputation rules described in [\[Reference Manual for Partial Data Imputation\]](#).

5.1.2 Study drug

If the date of administration of study treatment during Treatment Period 1 is missing or partial, it will be imputed as the date of the Day 1 visit.

If the date of administration of study treatment during Treatment Period 2 is missing or partial, it will be imputed as the date of the Week 52+ 1 Day visit.

5.1.3 Missing HFMSE and RULM item scores

For the HFMSE, if 6 or fewer items are missing, the missing items will be imputed to be 0 prior to the calculation of the total score of HFMSE. If more than 6 items are missing at an assessment time point, the total score of HFMSE at this assessment time point will not be calculated and will be left as missing.

For the RULM, if 3 or fewer items are missing, the missing items will be imputed to be 0 prior to the calculation of the total score for RULM. If more than 3 items are missing at an assessment time point, the total score of RULM at this assessment time point will not be calculated and will be left as missing.

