- Obtaining a complete HFMSE assessment that is a true representation of the participant's motor ability is critical in order to appropriately investigate OAV101 efficacy. The completeness of the HFMSE assessment has been considered in Type 2 SMA motor assessment analyses, thus allowing for fair and valid assessment of motor abilities (Mercuri et al 2019, Coratti et al 2020b). Every effort should be made to administer all scale items appropriately following scale criteria. In the event that an item is not able to be administered, a 'Cannot Test' (CNT) is marked for that item. To ensure the patient's true motor ability is being represented, rescheduling of the assessment administration is warranted when any factor significantly impedes the participant's ability to perform the motor assessment which includes behavior issues (e.g., tantrums, inconsolable), refusal to participate in testing, transient pain, fractures, intercurrent surgery, or recent pneumonia or other infections. **CCI** [REDACTED]

[REDACTED] Study specific requirements around HFMSE administration requirements are outlined below. Based on prior experience in the open label AVXS-101-CL-102 clinical trial of intrathecal OAV101, very few incomplete assessments are anticipated.

Contractures: It is important to note that contractures alone do not exclude participants from being scored on the HFMSE. The impact of contractures on some assessment items needs to be established, therefore the therapist should indicate "limited by contracture". However, participants with severe contractures, which limit their ability to be positioned in prone during Screening, are not eligible (exclusion criterion 13).

HFMSE at Screening

- In order to assess trial eligibility, an HFMSE assessment with total score must be obtained during the Screening period ([Section 5.1](#)).
- Two HFMSE assessments are performed during the screening period. Although two complete HFMSE assessments is preferred at Screening, a minimum of one assessment with total score must be obtained.
- Rescheduling of the assessment administration within the screening window is required if an HFMSE assessment with a total score is unable to be obtained.

HFMSE assessment at baseline and post-OAV101 administration/sham procedure to Week 64 (End of Study)

- HFMSE is administered at each visit specified in the Schedule of Assessments ([Table 8-1](#)).

HFMSE assessment **CCI** [REDACTED]

[REDACTED]
[REDACTED]
[REDACTED]
[REDACTED]
[REDACTED]

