2.1.1 General definitions

Study treatment is OAV101 (1.2x10¹⁴ vector genomes) or sham administration.

The **date of first administration of study treatment** is defined as the date of OAV101/sham administration during Treatment Period 1.

The **date of second administration of study treatment** is defined as the date of OAV101/sham administration during Treatment Period 2.

Study day is the number of days since the date of first administration of study treatment for period 1 and number of days since the date of second administration of study treatment for period 2.

- Study day 1 is the date of the first administration of study treatment during Treatment Period 1 and the date of second administration of study treatment during Treatment Period 2 .
- Study day of date X = date X – date of first administration of study treatment during Treatment Period 1 + 1 if date X is on or after the date of first administration of study treatment during Treatment Period 1.
- Study day of date X = date X – date of first administration of study treatment during Treatment Period 1 if date X is before the date of first administration of study treatment during Treatment Period 1. Study days before the first study treatment administration during Treatment Period 1 will have the prefix “-”.

Baseline is defined as follows:

- **HFMSE**: Baseline value for HFMSE (i.e., total or individual item) score is defined as the average of HFMSE (i.e., total or individual item) score used for stratification (maximum of all available values before baseline visit) and the measurement or evaluation made at the baseline visit prior to the first administration of study treatment during Treatment Period 1, assuming both values have complete and valid scores available. If just one of the above mentioned values (score used for stratification and baseline visit measurement) has a complete and valid score available, then the baseline HFMSE (i.e., total or individual item) score is defined as the single available value.

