- **RULM**: Baseline value for RULM total score is defined as the average of all non-missing assessments prior to the first administration of study treatment during Treatment Period 1, assuming all assessments have complete and valid total scores available. If two of the assessments have a complete and valid total score available, then the baseline RULM total score is defined as average of the two available assessment scores. If just one of the assessments has a complete and valid total score available, then the baseline RULM total score is defined as the single total score available.
- **Other assessments**: The latest non-missing measurement or evaluation made prior to the first administration of study treatment during Treatment Period 1.

Change from baseline is defined as post-baseline value minus baseline value.

For HFMSE and RULM, the **End of Follow-up Period 1** assessment is defined as the average of the Week 48 and Week 52 assessments, assuming both assessments have complete and valid total / individual scores available. If just one of the assessments collected at these two visits has a complete and valid total / individual score available, then the end of Follow-up Period 1

assessment is defined as the single assessment total / individual score collected at Week 48 or Week 52.

Last participation day can be calculated using end of participation date – date of second administration of study treatment + 1.

Inexact values will be handled as follows.

- If a laboratory value is recorded/reported as “>X”, “≥X”, “- If an antibody titer value is reported as <12.5, a value of 0.5×12.5 will be used and if ≥ 819200 is reported, a value of 1.5×819200 will be used for analysis purposes. The originally recorded values will be displayed in corresponding listings.

An **Adverse Event** (AE) is any untoward medical occurrence in a clinical investigation participant, which does not necessarily have a causal relationship with the drug or device under study.

A Treatment Emergent Adverse Event (TEAE) is any AE whose onset or worsening occurred after dosing on Day 1 till the end of follow-up period 2.

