Week 56	Week 4	Day 29	Day 1	Day 43
Week 60	Week 8	Day 57	Day 44	Day 71
Week 64	Week 12	Day 85	Day 72	Last participation day

CCI [REDACTED]

CCI [REDACTED]

[figure not shown]
CCI

CCI

CCI

CCI

CCI

CCI

Troponin-I, Echocardiogram and ECG:

Period 1 windows:

Visit	Nominal day	Start day	End day
Week 1	Day 8	Day 1	Day 18
Week 4	Day 29	Day 19	Day 43
Week 8	Day 57	Day 44	Day 71
Week 12	Day 85	Day 72	Day 127
Week 24	Day 169	Day 128	Day 253
Week 48	Day 337	Day 254	Day 351 [#]
Week 52*	Day 365	Day 352	Week 52 + Day 1 – 1

* Only applicable for ECG

For troponin-I and echocardiogram, the end day for Week 48 will be Week 52 + Day 1 – 1 instead of 351

Period 2 windows:

Visit (OAV-SHAM)	Visit (SHAM-OAV)	Nominal day	Start day	End day
Week 53	Week 1	Day 8	Day 1	Day 18
Week 56	Week 4	Day 29	Day 19	Day 43
Week 60	Week 8	Day 57	Day 44	Day 71
Week 64	Week 12	Day 85	Day 72	Last participation day

If more than one observation is included in a time window for HFMSE and RULM, irrespective of the observations being scheduled or unscheduled, the latest observation will be used in analyses.

For other endpoints, when an assessment value for both a scheduled visit and an unscheduled visit are present within the same analysis window, the scheduled visit value will be used. Unscheduled visit data will only be used when there is no measurement from the scheduled visit in the defined window.

If more than one scheduled observation for a specific assessment is included in a time window, the assessment closer to the nominal time will be used. If there are two scheduled observations equally distant to the nominal time, the latest one will be used in analyses.

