2.5.5 Sensitivity analyses

In order to assess the potential impact of excluding participants from the primary analysis who are randomized into the study but did not receive treatment, the primary efficacy analysis will be repeated using the ITT Set.

In order to assess the potential impact of missing HFMSE data, sensitivity analyses will also be conducted using the FAS, where missing data will be imputed using multiple imputation (MI) methodology, if there are more than 5% of patients (≥ 7 participants) in the FAS missing end of follow-up period 1 HFMSE data. MI analysis with both the missing at random (MAR) and the missing not at random (MNAR) assumption will be performed. For MI with MNAR assumption, a tipping-point analysis will be performed using pattern-mixture model with a delta-adjusted pattern imputation. These specific imputation methods are further described in [Section 5.1.4](#) of this SAP.

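### Does scoring up to 6 unscored HFMSE items as 0 leave the primary endpoint undefined, given that 2.1.1 averages only complete and valid scores?

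*SAP*

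**What the plan says.** - SAP 5.1.3: for the HFMSE, "if 6 or fewer items are missing, the missing items will be imputed to be 0" and a total is then calculated. "If more than 6 items are missing at an assessment time point", there is no total for that time point. The RULM rule is the same with a limit of 3.
- SAP 2.1.1: the HFMSE baseline averages the score used for stratification and the baseline-visit score, "assuming both values have complete and valid scores available". End of Follow-up Period 1 averages Weeks 48 and 52, "assuming both assessments have complete and valid total / individual scores available". If only one score qualifies, it is used alone.
- SAP 2.1.2: when an HFMSE or RULM window holds several observations, then "irrespective of the observations being scheduled or unscheduled, the latest observation will be used in analyses".
- SAP 2.5.5: multiple imputation is run if more than 5% of participants (7 or more) are "in the FAS missing end of follow-up period 1 HFMSE data". Under 5.1.4.1 the tipping-point shift applies only to values imputed in that analysis.
- Protocol 8.3.1.1: "In the event that an item is not able to be administered", it is marked Cannot Test. The section asks for the assessment to be rescheduled when something significantly impedes performance, and states that "very few incomplete assessments are anticipated".

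**The concern.** In ordinary English an assessment with unscored items is not complete. On that strict reading, a zero-filled total at Week 48 drops out and Week 52 stands alone. On the looser reading the two are averaged. Two programmers could then derive different primary-endpoint values from the same data.

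The direction of error also depends on timing. A zero-filled score at Week 48 or 52 lowers the change, and one at Day -1 lowers baseline and raises the change, so the zero rule is not uniformly conservative. Either can move a child across the responder threshold.

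Other rules do not obviously catch this. The window rule ignores completeness. On the looser reading a zero-filled total counts as observed, so neither the imputation trigger nor the tipping-point shift reaches it.

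**Working it through.** **1. Which reading does the text support?** SAP 5.1.3 says when a total exists and when it is left missing, without limiting this to certain visits. On the strict reading it could never supply a baseline or Week 48/52 value and would serve only intermediate visits. SAP 2.1.1 falls back to whichever single score is available. Protocol section 3 ties completing an assessment to obtaining a total score. Together these favour one reading: a score qualifies if 5.1.3 lets it be calculated.

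**2. The plan's own power figure.** Inputs from SAP section 3: 75 and 50 participants, difference 3, SD 5, two-sided alpha 0.05. Standard error = 5 × √(1/75 + 1/50) = 0.913. Noncentral t power = 0.903, which matches the stated 90%.

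**3. Ceiling for one child.** HFMSE items score 0 to 2, so 6 items × 2 = 12 points at one visit. Averaged over two visits this is 12/2 = 6; it stays 12 if that visit is the only one available. For the RULM, 3 × 2 = 6 points, giving 6/2 = 3 over two assessments or 6/3 = 2 over three.

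**4. Expected error for one child.** Assume the 6 unscored items are a random sample of the 33 and the true total is T. The averaged error is 6 × T/33/2.

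| T (assumed) | Averaged error |
|---|---|
| 10 | 0.91 |
| 20 | 1.82 |
| 30 | 2.73 |

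The error is near 0 if the unscored items are ones the child would fail anyway.

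**5. Effect on the comparison, both arms alike.** The documents give no frequency, so assume a share p of each arm carries an averaged error e. The difference in means is unchanged, and the variance becomes 25 + p(1−p)e².

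| p | e | Variance | Power |
|---|---|---|---|
| 0.05 | 2.73 | 25.35 | 0.899 |
| 0.10 | 2.73 | 25.67 | 0.896 |
| 0.10 | 3 | 25.81 | 0.894 |
| 0.10 | 6 | 28.24 | 0.866 |

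At the largest expected error, and with 10% affected, the loss is 0.903 − 0.896 = 0.007. The last row needs every affected child to be at the ceiling.

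**6. One child at the ceiling.** The OAV101 mean moves by 6/75 = 0.08 or the sham mean by 6/50 = 0.12, compared with a standard error of 0.913. A changed responder status moves a proportion by 1/75 = 1.3 or 1/50 = 2.0 percentage points.

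**7. What an unequal rate would do.** If only the OAV101 arm were affected, with p = 0.05 and e = 3, the difference would shrink by 0.15 and power would be 0.872. If only the sham arm were affected at the same rate, the type I error would be 0.053. Nothing in the design points to such an imbalance.

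**The case for a change.** The textual point stands: on the visible wording the term is undefined, the two sections do not cross-refer, and no listed analysis varies the item rule. The available safeguards are partial. Using the maximum screening score protects only half of the HFMSE baseline, and protocol section 3 requires no repeat at Day -1. The protocol itself treats a complete assessment as critical to judging efficacy, and a definition plus one sensitivity run would be cheap.

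Several things weaken the case for acting.

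- **Hidden text.** Parts of protocol 8.3.1.1 and 8.3.1.2 are blacked out. The text of 12.4.1, to which Table 2-1 sends the reader for the endpoint definition, is not in the public copy, nor are 12.4.4 and 12.4.5. A definition may be there. That Cannot Test items count as missing is also an inference.
- **The imputation argument depends on the reading.** On the strict reading, a child with no complete Week 48 or 52 score has no endpoint and does count toward the 5% trigger. Neither reading leaves a child without a rule.
- **The window rule fits the design.** Because impeded assessments are to be rescheduled, the later observation is usually the intended repeat. A full test followed by a partial one is the unusual order.
- **Requiring every item has a price.** A visit with 32 of 33 items scored would be thrown away. Baseline could rest on the maximum screening score alone, and the Week 48/52 average, meant to dampen variability, would be lost for that child.

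**Conclusion.** No change is needed. This is a detail left unstated that a programmer can settle sensibly from the surrounding text: a total calculable under 5.1.3 enters the averages. Followed that way, the plan still supports a sound primary conclusion. One child's averaged HFMSE change can be wrong by up to 6 points, but if the arms are affected alike the loss of power is under one percentage point, even with 10% of each arm carrying the largest expected error of 2.73 points.

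This rests on three assumptions: incomplete assessments are as rare as the protocol expects, unscored items are not concentrated in one arm, and unscored items are not mainly ones the child could fully perform. Blinded assessors and a baseline taken before treatment support the second. A stricter definition would trade one small error for another, and extra counts or a further sensitivity run would not be expected to alter the conclusion.
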